## Abstract

Myocardial injury is the most common cause of death in the 30 days after non-cardiac surgery. Hypothermia increases sympathetic activation, promotes tachycardia, and causes hypertension — all of which may increase the risk of myocardial injury. Only one small study evaluated the relationship between moderate hypothermia and myocardial infarction, and was unable to make definitive conclusions. Moderate perioperative hypothermia is now uncommon, but mild hypothermia ( $\approx 35.5^{\circ}\text{C}$ ) remains common. Whether aggressive warming to a truly normothermic level ( $\approx 37^{\circ}\text{C}$ ) improves outcomes remains unknown. We therefore propose to test the primary hypothesis that aggressive warming reduces the incidence of major cardiovascular complications. Up to 5,058 patients will be randomly assigned to routine care (core temperature  $\approx 35.5^{\circ}\text{C}$ ) or aggressive warming ( $>37^{\circ}\text{C}$  core temperature) in a multi-center trial. Patients will be randomly: 1) **routine thermal management** with rescue intraoperative forced-air warming to prevent core temperature from decreasing to less than  $35.5^{\circ}\text{C}$ ; or, 2) **aggressive warming** to a target final intraoperative core temperature between  $37$  and  $37.5^{\circ}\text{C}$ . The **primary outcome** will be a composite of myocardial injury (troponin elevation, apparently of ischemic origin), non-fatal cardiac arrest, and all-cause mortality within 30 days of surgery. **Secondary outcomes**, also within 30 days, will include: 1) 30-day deep or organ-space surgical site infection, as defined by Center for Disease Control criteria; 2) intraoperative transfusion requirement, defined as units of red blood cells transfused; 3) duration of hospitalization; and, 4) readmission within a month of surgery.

## Trial Management

Trial management will include an Executive Committee, a broader Steering Committee, and a Data and Safety Monitoring Board (DSMB) consisting of experienced trialists who have no other involvement in the study. The Steering Committee will advise the Executive Committee and Principle Investigator, as will the DSMB. Normally, the DSMB will evaluate blinded results (Group A vs. Group B) at each interim analysis, and at other intervals as they see necessary. The DSMB may request unblinded results if there is a safety concern.

## Background

In recent decades, intraoperative mortality has decreased by a factor-of-ten, even though we now care for much sicker and older patients. Preventable anesthetic-related intraoperative mortality is now so rare that it is hard to quantify. Postoperative mortality, in contrast, remains substantial. Overall 30-day postoperative mortality is about 1% in the United States, and about 2% amongst inpatients (outpatients die much less frequently). To put this mortality in perspective, if the postoperative period were considered a disease, it would represent the third leading cause of death in the United States. Roughly a quarter of all 30-day postoperative deaths are cardiovascular, or consequent to cardiovascular events — with myocardial injury being by far the most common.

Worldwide, 8% of surgical inpatients >45 years of age have a postoperative myocardial injury as defined by a troponin elevation that is due to an ischemic etiology, with only 22% of these events fulfilling the diagnostic criteria of the universal definition of myocardial infarction. Only 7% of patients experiencing a perioperative myocardial infarction will have chest pain, and 65% are entirely clinically silent which means that they will go undetected without routine troponin screening.

It is tempting to dismiss asymptomatic biomarker elevation as “troponitis” and assume that it is inconsequential; however, this would be a mistake because 30-day mortality in patients with elevated postoperative troponin is significantly and substantially increased *with and without* symptoms. The term Myocardial Injury after Non-cardiac Surgery (MINS) recognizes that troponin elevations without a non-ischemic explanation (e.g., sepsis, pulmonary embolus) are clinically important — even in patients whose symptoms and signs do not meet the formal definition of a myocardial infarction.

Mortality at 30 days in patients with MINS is a concerning 10%, which represents a five-fold increase from background risk. Mortality increases exponentially as a function of peak postoperative troponin concentration, ranging from 9% for fourth-generation troponin T plasma concentrations of 0.03-0.29 ng/ml to 17% for concentrations  $\geq 0.3$  ng/ml. Moreover, it is not just mortality that is increased: a composite of nonfatal cardiac arrest, congestive heart failure, stroke, and death occurred at a rate of 2.4% in patients without MINS and 18.8% amongst those with MINS, a factor-of-eight increase. The corresponding thresholds for generation five, high-sensitivity troponin T are  $\geq 20$  ng/L with at least a 5 ng/L increase from baseline, or troponin  $\geq 65$  ng/L with or without an increase from baseline. When postoperative troponin concentrations are between 65 and 1,000 ng/L, mortality is increased 70-fold.

It is thus reasonable to ask what perioperative factors might contribute to MINS. Among the likely candidates is hypothermia. Moderate perioperative hypothermia (e.g., 34.5°C) has been shown to cause surgical site infection, coagulopathy, reduced drug metabolism, prolonged postoperative recovery, and thermal discomfort. Thermoregulatory vasoconstriction, a response to hypothermia, increases systemic vascular resistance and consequently causes hypertension. When combined with thermal discomfort and shivering, hypothermia also causes tachycardia.

Among the major complications of hypothermia, myocardial outcomes are least well established. A recent observational analysis suggests an association between SCIP-10 compliance on temperature and cardiovascular outcomes. A single-center randomized trial of 300 patients evaluated cardiac outcomes, and the study was seriously under-powered. For example, only two hypothermic patients had a cardiac arrest and one had a myocardial infarction *versus* none in the normothermic group (36.7°C). Ten hypothermic patients experienced cardiovascular events *versus* two in normothermic patients. These fragile results, based on fewer than ten outcome events, are nearly as likely to be wrong as right, and a poor basis for health policy. The other relevant study had only 100 patients and was thus even more fragile.

An additional limitation of Frank *et al* is that diagnosis was primarily based on Holter ECG finding rather than troponin concentrations which are much more sensitive. Consequently, the overall myocardial infarction rate was <1% where the true rate is no less than 10% in vascular surgery patients. It is highly questionable whether any conclusion about hypothermia and myocardial outcomes can be derived from a study that missed 90% of the presumed myocardial events. The only other relevant trial was restricted to just 100 patients leaving it even less powered to detect clinically important outcomes. There thus remains considerable doubt as to the true effect of moderate hypothermia on cardiovascular outcomes.

An additional issue is that perioperative normothermia is often defined as a core temperature  $\geq 36^{\circ}\text{C}$ . The difficulty is that  $36^{\circ}\text{C}$  is *never* a normal temperature in humans. Even at the circadian nadir, usually about 3:00 AM, core temperature is not normally below  $36.5^{\circ}\text{C}$ ; and at about 3:00 PM, core temperature is typically about  $37.5^{\circ}\text{C}$ . On average, then, normal body temperature in humans is about  $37^{\circ}\text{C}$ , not the  $36^{\circ}\text{C}$  that is widely accepted as suitable for perioperative patients.

At any given time of day, core temperature is actively controlled by the thermoregulatory system. In other words, circadian temperature changes are not passive responses to environmental perturbations — which suggests that humans function best at temperature near  $37^{\circ}\text{C}$ . Consistent with this theory, randomized trials have shown that mild perioperative hypothermia causes coagulopathy, increased blood transfusion, surgical site infection, delayed drug metabolism, prolonged recovery, and prolongs the duration of hospitalization.

We therefore propose to test the hypothesis that aggressive warming to  $>37^{\circ}\text{C}$  core temperature, versus typical thermal management ( $\approx 35.5^{\circ}\text{C}$ ) prevents major adverse cardiac events, defined as 30-day myocardial injury (troponin elevation), non-fatal cardiac arrest, and all-cause mortality. Secondary outcomes will include infection, transfusion, duration of hospitalization, and hospital re-admission within 30 days.

## Methods

This will be a multicenter, international, randomized clinical trial. The trial will be coordinated by the department of OUTCOMES RESEARCH in Cleveland Clinic, Ohio, USA. About 200 people will be enrolled at the Cleveland Clinic. About 5,058 patients will participate at about ten Chinese hospitals.

### Inclusion Criteria

Consenting patients will be eligible if they are:

1. Scheduled for major noncardiac surgery expected to last 2-6 hours;
2. Having general anesthesia;
3. Expected to require at least overnight hospitalization;
4. Expected to have >50% of the anterior skin surface available for warming;
5. Age over 45 years;
6. Have at least one of the following risk factors:
  - a. Age over 65 years;
  - b. History of peripheral arterial surgery;
  - c. History of coronary artery disease;
  - d. History of stroke or transient ischemic attack;
  - e. Serum creatinine >175  $\mu$ mol/L (>2.0 mg/dl);
  - f. Diabetes requiring medication;
  - g. Hypertension requiring medication;
  - h. Current smoking.

### Exclusion Criteria

Patients will be ineligible if they:

1. Have a clinically important coagulopathy in the judgement of the attending anesthesiologist;
2. Are septic (clinical diagnosis by the attending anesthesiologist);
3. Body mass index exceeding 30 kg/m^2;
4. End-stage renal disease requiring dialysis;
5. Surgeon believes patient to be at particular infection risk.

## Measurements

Baseline demographic and morphometric characteristics will be recorded, including height, weight, and sex. Cardiovascular risks will be recorded, including hypertension requiring treatment, diabetes requiring oral medications or insulin, end-stage renal disease requiring dialysis, history of previous myocardial infarction, congestive heart failure, chronic obstructive pulmonary disease, and smoking status. Cardiovascular medications will be similarly recorded, including beta blockers, angiotensin converting enzyme inhibitors, angiotensin receptor blockers, and statins.

Type of surgery will be characterized as orthopedic, laparoscopic, open abdominal, neurosurgical (including spine), and other. Timing will be characterized as elective, urgent, or emergent. To characterize the risk of surgical site infection, we will record whether the operation involved colon resection, rectal resection, other abdominal surgery, and whether the wound was contaminated or dirty-infected.

Intraoperative core temperature will be measured in the distal esophagus, nasopharynx (10-20 cm past the nares), or pulmonary artery. Temperature will be recorded at 15-minute intervals throughout surgery. Mean-arterial pressure and heart rate will also be recorded at 15-minute intervals throughout surgery. Mean arterial pressure and heart rate will also be recorded at 15-minute intervals for the initial postoperative hour.

It will be impossible to blind patients to prewarming and intraoperative clinicians and investigators to group assignment. However, all postoperative measurements will be made by investigators who are unaware of patients' group assignment and intraoperative management. The study will thus be *assessor blinded*. To maintain blinding, the anesthesia record will be sealed in an opaque envelope before patients leave the post-anesthesia care unit. The envelope will be marked "Do not open until [date 35 days after surgery]." Some hospitals will have electronic records; in those cases, we will ask investigators evaluating postoperative outcomes not to access the anesthesia record.

Blood for generation 4 or 5 troponin T, or troponin I (per clinical routine) will be recorded preoperatively up to 2 weeks prior to day of surgery, and on the first two postoperative days so long as patients remain hospitalized. Troponin samples will also be obtained if patients have shortness of breath or experience chest, neck, or arm pain. Blood troponin concentrations exceeding site thresholds (depending on individual types of troponin tests) should prompt cardiology consultation, an electrocardiogram, and if possible, an echocardiogram. Hemoglobin will also be obtained on the first postoperative morning. Other preoperative laboratory values and relevant testing will be recorded if available (but are not required per protocol), including hemoglobin, creatinine, and blood troponin concentrations after the mandated initial two postoperative days.

Quality-of-recovery 15 will be assessed on the third postoperative day in person or by phone in patients already discharged. A Chinese version of the Quality-of-recovery instrument has been validated. If discharged patients cannot be reached on the third postoperative day, attempts will be made on the fourth postoperative day. Patients will also be evaluated for various outcomes on the day of hospital discharge and 30 days after surgery, with a +5-day window. That is, attempts to contact patients will begin about day 30 and continue through postoperative day 35. The study will be censored at day 30, even if patients remain hospitalized.

For patients with a chronic elevation or an acute myocardial injury before surgery, a new myocardial injury after surgery requires identification of a new elevated troponin after surgery as per points 1-5 above, and the troponin elevation must be a 20% rise beyond the chronic troponin value or beyond the last measurement of the acute preoperative myocardial injury that was clearly demonstrated to have peaked and was coming down. Patients meeting diagnostic criteria for MINS will be evaluated for myocardial infarction with EKG and ECHO with cardiac consultation, which will help us detect all infarctions and increase the baseline incidence.

**Secondary outcomes** will include:

- 1) 30-day deep or organ-space surgical site infection, as defined by Center for Disease Control criteria\*;
- 2) Intraoperative transfusion requirement, defined as units of red blood cells transfused;
- 3) Duration of hospitalization (censored at 30 days);
- 4) Readmission within a month of surgery;

Exploratory outcomes will be:

- 1) Estimated intraoperative blood loss;
- 2) The change in blood hemoglobin from preoperatively to the first postoperative morning;
- 3) 30-day superficial surgical site infection;
- 4) Quality-of-recovery 15 on the third postoperative day in person or by phone in patients already discharged;
- 5) 30-day myocardial infarction meeting requirements of the Third Universal Definition.

\*Definitions of surgical site infections, modified from 1990 CDC criteria: <http://www.cdc.gov/hicpac/SSI/table1-SSI.html>.

## 1. Superficial infection

Infection involves only skin or subcutaneous tissue of the incision *and* at least *one* of the following:

- Purulent drainage from the superficial incision.
- Organisms isolated from culture of fluid or tissue from the superficial incision.
- At least one of the following signs or symptoms of infection: pain or tenderness, localized swelling, redness, or heat *and* superficial incision is deliberately opened by surgeon, *unless* incision is culture-negative.
- Diagnosis of superficial incisional SSI by the surgeon or attending physician.

## **2. Deep infection**

Infection appears to be related to the operation *and* infection involves deep soft tissues (e.g., fascial and muscle layers) of the incision *and* at least *one* of the following:

- Purulent drainage from the deep incision but not from the organ/space component of the surgical site.
- A deep incision spontaneously dehisces or is deliberately opened by a surgeon when the patient has at least one of the following signs or symptoms: fever ( $>38^{\circ}\text{C}$ ), localized pain, or tenderness, unless site is culture-negative.
- An abscess or other evidence of infection involving the deep incision is found on direct examination, during reoperation, or by histopathologic or radiologic examination.
- Diagnosis of a deep incisional SSI by a surgeon or attending physician.

## **3. Organ-space infection**

Infection involves any part of the anatomy (e.g., organs or spaces), other than the incision, which was opened or manipulated during an operation[S6] *and* at least *one* of the following:

- Purulent drainage from a drain that is placed through a stab wound‡ into the organ/space.
- Organisms isolated from an aseptically obtained culture of fluid or tissue in the organ/space.
- An abscess or other evidence of infection involving the organ/space that is found on direct examination, during reoperation, or by histopathologic or radiologic examination.
- Diagnosis of an organ/space SSI by a surgeon or attending physician.

Outcomes will be centrally adjudicated by investigators blinded to randomization and intraoperative core temperatures.

Data will be recorded on case-report forms and directly entered via a web site into a secure REDCap database (i.e., with a tablet computer). All HIPAA rules will be followed; no identified data from remote sites will be entered into REDCap, and no Clinic data will be sent elsewhere. We will request a copy of the anesthesia record, redacted for

protected health information, for auditing purposes. Similarly, we will request redacted copies of key lab tests and records related to defined outcomes.

## Statistical Plan

Reported temperatures will include time-weighted average, minimum, and final intraoperative core temperatures.

Analyses will be modified intent-to-treat, including all randomized patients who received treatment (i.e., patients randomized but not receiving treatment will not be included in any analyses). Randomized groups will be compared on baseline and demographic characteristics using absolute standardized difference, defined as the absolute difference in means, mean ranks, or proportions divided by the pooled standard deviation. All analyses will adjust for any imbalanced baseline characteristics between randomized groups, defined as the maximum of 0.10 and absolute standardized difference  $> 1.96 \times \sqrt{\frac{1}{n_1} + \frac{1}{n_2}}$ .

Missing outcomes will be imputed using an appropriate method, after examining the missing mechanism and drop-out rates. If less than 5% of data are missing, we will assign worst outcome to the active treatment group and best outcome to the control group for patients missing all records of MINS, non-fatal cardiac arrest and mortality; we will apply the last observation carried forward (LOCF) method for patients missing 30-day follow-up data but having discharge assessment. If missing is 5~20%, we will use the multiple imputation method.

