### *Primary analysis*

We will assess the effect of warming strategy on the binary-event composite of myocardial injury, non-fatal cardiac arrest, and all-cause mortality within 30 days of surgery, using a multivariate generalized estimating equations (GEE) method. A common effect GEE test with an unstructured working correlation matrix will be performed, assuming that each component is similarly affected by intervention. The treatment-by-component interaction will be examined in a separate distinct effects GEE model to assess the heterogeneity of the treatment effect across outcomes.

Secondly, we will estimate the average relative effect of aggressive warming across the three categories of complications, using a GEE 'distinct effects' model with an unstructured working correlation matrix. This method is not driven by component with the highest frequency but may have a lower power compared to common effects model because one complication has a lower expected incidence. Regardless of the existence of the interaction, we will report the treatment effect of aggressive warming for each complication. The significance criterion will be 0.017 for each association (i.e., 0.05/3, Bonferroni).

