### *Secondary analyses*

The effect of warming strategy on collapsed composite of 30-day deep or organ-space surgical site infection and readmission within a month of surgery will be assessed using separate chi-square tests or multivariable logistic regression models, as appropriate.

The effect of warming strategy on the intraoperative transfusion requirement, defined as units of red blood cells transfused, will be assessed using a multivariable Poisson or negative binomial regression model, as appropriate.

Finally, the effect of warming strategy on time to discharge alive will be assessed using a Cox proportional hazards regression model. Patients who died before discharge will be assigned a censoring time equal to the longest observed duration of hospitalization.

To assess the robustness of our primary analysis, we will conduct per-protocol analysis for primary outcome by analyzing the subset of patients who completed the treatment originally allocated and without missing outcome data. This analysis is expected to be biased in favor of the preferred treatment and therefore no inference will be made about results.

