### **Sample-size Estimate**

[figure not shown]
Amongst 10,000 patients enrolled in POISE-2, 8,449 met the inclusion criteria proposed for PROTECT. The incidence of MINS, nonfatal cardiac arrest, and total mortality within 30 days post-operatively were 10%, 0.1% and 1% respectively. These studies were largely conducted outside the United States and we can thus assume that most patients were either unwarmed or inadequately warmed. We will thus assume that patients assigned to routine management will have a similar incidence of our composite outcome.

A total of 4000 patients will give a power of 0.9 at the 0.05 significance level to detect a 30% or more relative reduction in the primary outcomes, comparing routine

thermal management group to aggressive warming group. Sample size was calculated for common effect GEE model with unstructured covariance matrix, assuming a correlation of 0.1 between outcomes. We estimated sample size using the MULTBINPOW SAS macro [Mascha EJ Power Calculation for Tests on a Vector of Binary Outcomes], which can estimate the power for multivariate GEE model given varying correlation and sample size.

After accounting for interim analysis at each 25% of the maximum enrollment (3 interim analyses and a final analysis, as needed), a maximum of 4802 patients would be needed (2401 per group) for the analysis.

For the primary analysis, we will use a group sequential design with a nonbinding beta boundary, employing a gamma spending function with parameter gamma of -4 for efficacy and 0 for futility, thus spending beta (for futility monitoring) considerably faster than alpha (for efficacy monitoring). Boundaries for efficacy (futility in parentheses) at the each interim and final analyses are  $P \leq 0.001$  ( $P > 0.880$ ),  $P \leq 0.005$  ( $P > 0.525$ ),  $P \leq 0.014$  ( $P > 0.169$ ), and  $P \leq 0.044$  ( $P > 0.044$ ), respectively, based on an anticipated 30% treatment effect. Figure 1 shows the z-statistic boundaries for efficacy and futility at each interim look.

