## Time Line

Study Procedure		Screening	Day of Surgery	POD 1	POD 2 e	POD 3 e	Discharge c	POD 30 d
Informed consent		X						
Inclusion/exclusion criteria		X	X					
Labs	Hemoglobin	X a	X a	X	X a	X a		
	Creatinine	X a						
	Troponin	X	X a	X	X	X a		
Procedures	ECG	X a	X a	X a	X a	X a	X a	X a
	ECHO	X a	X a	X a	X a	X a	X a	X a
	Cardiac Catheterization		X a	X a	X a	X a	X a	X a
Intraoperative Data			X					
Cardiovascular morbidity/mortality survey				X	X	X	X	X
QOR15						X b		
Surgical Site Infection survey							X	X

 Council for International Organizations of Medical Sciences (CIOMS) (2002). Commentary on Guideline 4 (Individual Informed Consent), Cultural considerations. *International Ethical Guidelines for Biomedical Research Involving Human Subjects*. [http://www.cioms.ch/frame\\_guidelines\\_nov\\_2002.htm](http://www.cioms.ch/frame_guidelines_nov_2002.htm).

- a: If available
- b: If patient is not reachable on day 3, survey can be completed on day 4
- c: If patient is discharged on postoperative days 1-3, complete forms for postoperative day and discharge
- d: If patient is not reachable on day 30, attempt to contact for consecutive 5 days
- e: Complete if patient is still in hospital

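### Below 5% missing, the planned imputation codes treated patients with no outcome record as worst in the warming arm and best in control; this biases the primary estimate against warming, and the worst outcome is not defined by component

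*Combined protocol and SAP*

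**What the plan says.** All analyses are restricted to randomized patients who received treatment. The Statistical Plan opens its missing-data paragraph by promising a suitable method chosen after looking at the mechanism and the dropout rates. It then fixes the rules by amount of missing data:

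- **Below 5%, no record of MINS, cardiac arrest or death:** "we will assign worst outcome to the active treatment group and best outcome to the control group for patients missing all records of MINS", with cardiac arrest and mortality named next.
- **Below 5%, discharge assessment present but 30-day follow-up absent:** last observation carried forward.
- **5–20%:** "If missing is 5~20%, we will use the multiple imputation method".

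Nothing labels the worst/best rule a sensitivity analysis. The one stated robustness check (Secondary analyses) is a per-protocol analysis in patients with complete outcomes, of which the plan says "This analysis is expected to be biased in favor of the preferred treatment and therefore no inference will be made about results".

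The primary test is a common-effect GEE on three binary components. Under Primary analysis the plan adds that "we will report the treatment effect of aggressive warming for each complication", each at 0.017. Which components the worst outcome sets to an event is not stated.

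**The concern.** The imputation depends on the arm. It adds events only to warming and non-events only to control, so the sign of the bias is known before any data are seen. A true benefit is diluted. With no true effect, the chance of an apparent harm rises, and the trial has a harm boundary (Figure 1) as well as futility boundaries.

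The plan also applies this one-sided method when little is missing and the more neutral multiple imputation when more is missing. The 5% that separates them has no stated unit (patients, outcome fields or visits).

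The rare components are the most exposed. At the assumed 1% mortality and 0.1% cardiac arrest, the control arm expects about 24 deaths and 2.4 arrests among 2,401 patients. A handful of imputed events can therefore change a component result, and two analysts following the plan could code those events differently.

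**Working it through.** **Inputs from the documents.** Control rates 10% (MINS), 0.1% (arrest) and 1% (death); 30% relative reduction; 2,401 per arm; final boundary P ≤ 0.044 (Sample-size Estimate); 0.017 per component (Primary analysis).

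**Assumptions.** *m* is the share of treated patients with no outcome record, equal in both arms; the documents give no value. Composite control risk is 10%. Harm boundaries mirror the efficacy boundaries, because the P-values listed after "Boundaries for efficacy (futility in parentheses) at the each interim and final analyses are" cover efficacy and futility only.

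**The plan's own figures.** A two-proportion calculation (10% vs 7%, two-sided 0.05, power 0.90) gives 3,628 patients against the stated 4,000; power at 4,000 is 0.926. The stated number is somewhat conservative, which does not affect this point. The sequential step does reproduce: inflation 1.194 gives 4,000 × 1.194 ≈ 4,775 against 4,802, with a final boundary of 0.0438 against 0.044.

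**1. Composite, single look at P ≤ 0.044** (z = 2.014, pooled two-proportion test)

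- Control risk after imputation: 0.10(1 − m)
- Warming risk, true RR 0.70: 0.07(1 − m) + m
- Warming risk, no true effect: 0.10(1 − m) + m

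At m = 0.003 the control risk is 0.0997 and the warming risk 0.07 × 0.997 + 0.003 = 0.07279. The RR is 0.07279/0.0997 = 0.73. The null and alternative standard errors are 0.008102 and 0.008093, so power = Φ[(0.02691 − 2.014 × 0.008102)/0.008093] = 0.905.

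| m | Per arm | RR | Power | Harm finding under the null (nominal 2.2%) |
|---|---|---|---|---|
| 0 | 0 | 0.70 | 0.96 | 2.2% |
| 0.1% | 2 | 0.71 | 0.94 | 2.9% |
| 0.3% | 7 | 0.73 | 0.905 | 4.8% |
| 0.5% | 12 | 0.75 | 0.85 | 7.5% |

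The null harm probability doubles at m = 0.27% (6.4 patients per arm). Power reaches 0.90 at m = 0.32% (7.7 per arm). Leaving out the same 12 per arm, with missingness unrelated to outcome, keeps the RR at 0.70 and power at 0.956, so the loss comes from the rule and not from the missing data. With an 11% control risk, power is 0.96, 0.94 and 0.90 at 0.1, 0.3 and 0.5%.

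**2. Four looks with the stated boundaries** (200,000 simulated trials per case, futility stopping applied). The documents do not say whether imputation applies at interim looks, so both readings are shown.

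| m | Power, every look | Null harm, every look | Power, final look only | Null harm, final look only |
|---|---|---|---|---|
| 0 | 0.925 | 2.0% | 0.925 | 2.0% |
| 0.1% | 0.91 | 2.6% | 0.92 | 2.4% |
| 0.3% | 0.86 | 4.3% | 0.89 | 3.3% |
| 0.5% | 0.80 | 6.7% | 0.86 | 4.3% |

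Without the third interim look, which the amendment log says was dropped, power with imputation at every look is 0.93, 0.91, 0.87 and 0.81 at m = 0, 0.1, 0.3 and 0.5%.

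**3. Common-effect GEE, single look** (RR 0.70 for each component, pairwise correlation about 0.1; power 0.96 with none missing). At m = 0.3% the result depends on what the worst outcome codes:

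| Coded as events | Power | Null harm |
|---|---|---|
| Death only | 0.93 | 3.9% |
| MINS only | 0.92 | 4.6% |
| All three | 0.905 | 5.7% |
| MINS and death | 0.87 | 7.0% |

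At m = 0.1% power is 0.94–0.95 and null harm 2.7–3.4%.

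**4. Rare components**

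- *Death, if coded:* RR = [0.007(1 − m) + m] / [0.01(1 − m)]. At m = 0.1% this is 0.007993/0.00999 = 0.80; at 0.3% it is 0.009979/0.00997 = 1.00. With no true effect, the chance of a significant excess of deaths at 0.017 (nominal 0.85%) is 1.6% with 2 imputed deaths and 6.3% with 7.
- *Arrest, if coded:* at m = 0.1%, RR = (0.0007 × 0.999 + 0.001)/(0.001 × 0.999) = 1.70 instead of 0.70.

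**The case against.** The strongest reply is that the affected group may be close to empty. Eligibility requires patients to be "Expected to require at least overnight hospitalization", troponin is drawn "on the first two postoperative days so long as patients remain hospitalized", and the Time Line schedules a "Cardiovascular morbidity/mortality survey" on postoperative days 1–3, at discharge and at day 30. Patients with a discharge assessment go to last observation carried forward. What remains is mainly early withdrawal or lost records. This stands: at 0–2 per arm the composite hardly moves, and the documents do not support any particular larger number.

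Second, the rule is conservative for the trial's hypothesis and cannot inflate a false claim of benefit. That is also true, but it is not conservative for the point estimate, the confidence interval, a harm finding or futility monitoring.

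Third, a fall in single-look power to 0.90 only returns the trial to its design power. That is fair for one look. With the planned looks and futility stopping, power at m = 0.3% is 0.86–0.89, although the futility boundary is nonbinding.

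Fourth, the opening sentence about choosing a suitable method leaves some discretion. It does, but the explicit rule for less than 5% follows it and is what an analyst would apply.

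Fifth, for a composite the worst outcome naturally means an event, and the per-protocol analysis gives a partial cross-check. The first part does not settle which of three separately modelled components is set to an event. The cross-check changes the population as well and carries no inference.

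**Conclusion.** The concern holds and should be fixed. Below 5% missing, the plan's stated method shifts the risk difference by about m against warming and leaves the coding of the three components undefined. The direction is certain whenever such patients exist. The size rests on an assumed m and is probably modest: negligible at 0–2 patients per arm, and noticeable from about 6–8 per arm, where the null harm probability doubles and single-look power falls to about 0.90. The mortality distortion requires both that the worst outcome include death and that about 7 warming patients lack any record. Shares of 1% or more (24 per arm; RR 0.80, single-look power 0.65) are extreme cases that the documents do not suggest. The missing definition of the worst outcome and of what the 5% counts is a gap whatever m turns out to be.

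**What to change.** - Use multiple imputation as the primary method below 5% as well, for treated patients with no outcome record.
- Keep worst/best as a labelled sensitivity or tipping-point analysis, and list which of MINS, arrest and death are coded as events.
- State what the percentage of missing data counts, and whether imputation applies at interim looks.
- Report the number of patients with no outcome record by arm.
- State that troponin not drawn because the patient had already gone home is not missing under the protocol and is not imputed.

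The cost is SAP wording and a little more analysis work; no extra patients are needed.
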